### **14. POTENTIAL BENEFITS TO SUBJECTS**

Laboratory studies, animal models of multiple myeloma and, the single patient detailed in Section 2.1 suggest that abatacept may be effective in reversing the resistance to chemotherapy, which is the major cause of treatment failure in patients. This could significantly enhance the therapeutic efficacy of the whole portfolio of agents currently used in the treatment of multiple myeloma. However, since abatacept is not an FDA approved drug for multiple myeloma, its effectiveness in humans is unknown.

Roswell Park Protocol No.: I 47217

Patients will be advised verbally and in a written consent form that this is a study of abatacept + ixazomib + dexamethasone, of which the type and likelihood of side effects are not known. Patients will be advised that the drugs used in this study may cause all, some, or none of the side effects listed in the consent and in the Package Inserts for the individual drugs. There may be other side effects of the drugs that we do not know about yet. They will be told that the side effects could be mild, moderate, or severe and that these side-effects could go away shortly after the treatment stops or, that they could be serious, long lasting, or may be permanent. They will be advised to notify their doctor right away about any side effects or problems that they experience while on this study and that this may decrease the chance that the side effects continue or become worse. If severe side effects develop, it may lead to their being taken off-study.

## **15. DATA AND SPECIMEN BANKING**

All samples for correlative analysis (blood and bone marrow aspirate) will be sent to DBBR for processing. All samples will be processed and stored in the DBBR laboratory ([name]). Samples will be used for planned study assays as well as for future analysis for other, yet to be identified biomarkers that may be related to clinical outcome. Any clinical data that is associated with the samples will be stored on a secured server in the Immunology Department, will be accessible only by the PI, Co-investigators, and PI-designated data manager and, will be password protected. All computer entry and networking programs will be done using PIDs only.

Any excess samples that remain following completion of the planned study correlates will continue to be stored in DBBR. A separate IRB approval will be obtained prior to any future research-related use of these banked samples.

**Note:** All investigator or analyzing research laboratories housing research samples need to maintain current Temperature Logs and study-specific Sample Tracking and Shipping Logs. The Principal Investigator/Laboratory Manager must ensure that the stated lab(s) have a process in place to document the receipt/processing/storage/shipping of study-related samples/specimens. This is required for both observational and interventional clinical studies collecting clinical samples.

## **16. MEASUREMENT OF EFFECT**

Disease response will be assessed for each group using criteria based on the **International Working Group Uniform Response Criteria** detailed in **Section 16.1**. If the only measurable parameter is serum immunoglobulins free light chain (FLC), the participant will be followed by **FreeLite™ Disease Response Criteria** provided in **Section 16.2. Measurable Disease Parameter** is provided in **Section 16.3**.

All response categories require two consecutive assessments made at any time before the institution of any new therapy; all categories also require no known evidence of progressive disease or new bone lesions if radiographic studies were performed. Radioactive studies are not required to satisfy these response requirements.

### 16.1. International Working Group Uniform Response Criteria

- **Stringent Complete Response (Stringent CR):** CR as defined below plus normal free light chain ratio and absence of clonal cells in bone marrow\* by immunohistochemistry or immunofluorescence\*\*

\*Confirmation with repeat bone marrow biopsy is not needed

\*\*Presence/absence of clonal cells is based upon the  $\kappa/\lambda$  ratio. An abnormal  $\kappa/\lambda$  ratio by immunohistochemistry and/or immunofluorescence requires a minimum of 100 plasma cells for analysis. An abnormal ratio reflecting presence of an abnormal clone is  $\kappa/\lambda$  of  $> 4:1$  or  $< 1:2$ .

- **Complete Response (CR):** Negative immunofixation on the serum and urine and disappearance of any soft tissue plasmacytomas and  $\leq 5\%$  plasma cells in bone marrow\*

\*Confirmation with repeat bone marrow biopsy is not needed.

- **Very Good Partial Response (VGPR):** Serum and urine M-protein detectable by immunofixation but not on electrophoresis or 90% or greater reduction in serum M-protein plus urine M-protein level  $< 100$  mg per 24 hours.

- **Partial Response (PR):**  $\geq 50\%$  reduction of serum M-protein and reduction in 24-h urinary M-protein by  $\geq 90\%$  or to  $< 200$  mg per 24 hours.

- If the serum and urine M-protein are unmeasurable, a  $\geq 50\%$  decrease in the difference between involved and uninvolved free light chain levels is required in place of the M-protein criteria.
- If serum and urine M-protein are unmeasurable, and serum free light assay is also unmeasurable,  $\geq 50\%$  reduction in plasma cells is required in place of M-protein, provided baseline bone marrow plasma cell percentage was  $\geq 30\%$ .
- In addition to the above listed criteria, if present at baseline, a  $\geq 50\%$  reduction in the size of soft tissue plasmacytomas is also required.

- **Stable Disease (SD):** Not meeting criteria for CR, VGPR, PR or progressive disease. This is not recommended as an indicator of response; stability of disease is best described by providing the time to progression estimates.

- **Progressive Disease (PD):** Increase of  $\geq 25\%$  of serum M-protein (which must also be an absolute increase of  $\geq 0.5$  g/dL) and/or urine M-protein (which must also be an absolute increase of  $\geq 200$  mg/24hr).

- If serum and urine M-protein are unmeasurable, there must be an absolute increase of  $\geq 100$  mg/L between involved and uninvolved FLC levels. PD is also measured by an absolute increase in bone marrow plasma cells  $\geq 10\%$ .
- In addition to the above listed criteria, progression may also be measured by a definite development of new bone lesions or soft tissue plasmacytomas or definite increase in the size of existing bone lesions or soft tissue plasmacytomas or, development of hypercalcemia (corrected serum calcium  $\geq 11.5$  mg/dL or 2.65 mmol/L) that can be attributed solely to the plasma cell proliferative disorder.

Roswell Park Protocol No.: I 47217

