##### **8.2. Secondary Endpoints**

- The NCI Common Terminology Criteria for adverse events (CTCAEv5.0) will be used to evaluate toxicity.

- Progression-free survival is defined as the time from the date of the first study treatment to the date of first observed disease progression or death due to any cause. Study participants will be followed every 3 months following end of treatment (until initiation of a new therapy or until death, whichever occurs first) to determine overall survival.

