### **11.2. Baseline Evaluations**

The following evaluations will be performed within 28 days prior to first dose of the study regimen unless otherwise specified:

- Complete history with pre-existing conditions (demographic information will also be recorded)
- Documentation of pathological diagnosis (see International Myeloma Working Group (IMWG) Diagnostic Criteria: Appendix D)
- Physical examination with vital signs (i.e., temperature, heart rate, respiratory rate, blood pressure) and weight. Height collected at baseline only.
- Skeletal survey, bone marrow MRI or PET/CT: Baseline evaluation should be completed within 8 weeks prior to first dose, and annually or as per local institutional guidelines
- Bone marrow biopsy/aspirate with flow cytometry for CD28 and CD86, molecular and cytogenetics, per investigator discretion. A fresh sample is not required if CD28 or CD86 positivity has been determined on a previous bone marrow aspirate or biopsy.

Roswell Park Protocol No.: I 47217

- An additional 20 mL of aspirate will be collected for isolation of multiple myeloma cells.
- Hematology: CBC with automated differentials
- Chemistry: CMP to include chloride, CO2, potassium, sodium, BUN, glucose, calcium, creatinine, total protein, albumin, total bilirubin, alkaline phosphatase, AST, ALT, A/G ratio, BUN/creatinine ratio, osmol (Calc), anion gap). In addition: phosphorus, magnesium, lactate dehydrogenase (LDH)
- Pregnancy test (serum) in females of childbearing potential: to be performed  $\leq$  7 days prior to start of study treatment.
- ECOG Performance Status (**Appendix A**)
- Disease Status Evaluation:
  - Blood:
    - Qualitative immunoglobulins:
    - SPEP
    - serum IFE
    - serum free light chain
  - Urine:
    - 24-hour UPEP and UIFE
- Blood draw for serum kynureanine and IL-6 levels
- Concomitant Medications: List any medications taken in the month prior to registration and any that will be discontinued within 1 week prior to first dose of the study regimen.

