## Appendix D IMWG Diagnostic Criteria

---

Presence of an M-componenta in serum and/or urine plus clonal plasma cells in the bone marrow and/or a documented clonal plasmacytoma

PLUS one or more of the following:b

Calcium elevation ( $>11.5 \text{ mg/dl}$ ) [ $>2.65 \text{ mmol/l}$ ]

Renal insufficiency (creatinine  $>2 \text{ mg/dl}$ ) [ $177 \mu\text{mol/l}$  or more]

Anemia (hemoglobin  $<10 \text{ g/dl}$  or  $2 \text{ g/dl} < \text{normal}$ ) (hemoglobin  $<12.5 \text{ mmol/l}$ c or  $1.25 \text{ mmol/l} < \text{normal}$ )

Bone disease (lytic lesions or osteopenia)

---

aIn patients with no detectable M-component, an abnormal serum FLC ratio on the serum FLC assay can substitute and satisfy this criterion. For patients, with no serum or urine M-component and normal serum FLC ratio, the baseline bone marrow must have  $\geq 10\%$  clonal plasma cells; these patients are referred to as having 'non-secretory myeloma'. Patients with biopsy-proven amyloidosis and/or systemic light chain deposition disease (LCDD) should be classified as 'myeloma with documented amyloidosis' or 'myeloma with documented LCDD,' respectively if they have  $\geq 30\%$  plasma cells and/or myeloma-related bone disease.

bMust be attributable to the underlying plasma cell disorder.

cNote: Hemoglobin of  $10 \text{ g/dl}$  is  $12.5 \text{ mmol/l}$  [or  $100 \text{ g/l}$ ].

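### The hypercalcemia criterion for progression (Section 16.1, repeated in Appendix D) pairs 11.5 mg/dL with 2.65 mmol/L, but the two are not the same calcium level

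*Combined protocol and SAP*

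**What the plan says.** **Progression.** Under Progressive Disease, Section 16.1 lists hypercalcemia beside bone lesions and plasmacytomas as a further way to establish progression. The threshold is a corrected serum calcium of at least 11.5 "mg/dL or 2.65 mmol/L) that can be attributed solely to the plasma cell proliferative disorder". The hypercalcemia must also have newly developed.

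**Where progression feeds in.** Section 8.2 runs progression-free survival (PFS) from first treatment "to the date of first observed disease progression or death due to any cause". Section 16 sets the condition on response: "all categories also require no known evidence of progressive disease or new bone lesions if radiographic studies were performed".

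**Diagnosis.** Appendix D gives calcium above 11.5 mg/dl, with above 2.65 mmol/l in brackets. For anemia it gives hemoglobin below 10 g/dl (SI figure 12.5 mmol/l) or 2 g/dl below normal (SI figure 1.25 mmol/l). Its footnote c repeats that 10 g/dl is 12.5 mmol/l and adds 100 g/l. Section 11.2 uses the appendix at baseline: "Documentation of pathological diagnosis (see International Myeloma Working Group (IMWG) Diagnostic Criteria: Appendix D".

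No section says which unit governs.

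**The concern.** An endpoint criterion should classify a patient the same way whichever unit the laboratory prints. This one gives two numbers for a single threshold, and they mark different calcium levels. An assessor working in mmol/L would apply a lower cut-off than one working in mg/dL.

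Calcium and albumin are in the chemistry panel on Day 1 of every cycle (Section 11.3), so the criterion can be checked often. The trial is multi-site (Sections 4 and 6). At stake are the date of a PFS event and, through the no-progression condition in Section 16, whether a later response can be counted.

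**Working it through.** **Inputs from the documents.** Calcium pair: 11.5 mg/dL and 2.65 mmol/L (Section 16.1, Appendix D). Hemoglobin pairs: 10 g/dl with 12.5 mmol/l, and 2 g/dl with 1.25 mmol/l (Appendix D). Creatinine pair, used as a control: 2 mg/dl with 177 µmol/l (Appendix D).

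**Inputs not in the documents.** Two physical constants are assumed: the molar mass of calcium, 40.08 g/mol (range tried 40.0 to 40.1), and of creatinine, 113.12 g/mol.

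**Step 1: try to reproduce the plan's calcium pair.** mmol/L = (mg/dL × 10) / molar mass.

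- 11.5 × 10 / 40.08 = 2.87 mmol/L (2.868 to 2.875 over the range), not 2.65.
- In reverse, 2.65 × 40.08 / 10 = 10.62 mg/dL (10.60 to 10.63), not 11.5.
- For the pair to agree, the molar mass would have to be 115 / 2.65 = 43.4 g/mol, well outside the range. Rounding does not explain the difference.

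**Step 2: size of the gap.** 11.5 − 10.62 = 0.88 mg/dL, and 0.88 / 11.5 is about 8%. In SI units, 2.87 − 2.65 = 0.22 mmol/L. A corrected calcium from about 10.62 to just under 11.5 mg/dL (2.65 to just under 2.87 mmol/L) meets the SI figure and misses the conventional one.

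**Step 3: control.** 2 mg/dl of creatinine is 20 / 113.12 × 1000 = 176.8 µmol/l, against 177 printed. The appendix therefore does mean its SI figures as equivalents, and the creatinine pair is right.

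**Step 4: hemoglobin.** This needs no outside constant.

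- From 2 g/dl = 1.25 mmol/l: 1.25 / 2 = 0.625 mmol/l per g/dl.
- From 10 g/dl = 12.5 mmol/l: 12.5 / 10 = 1.25 mmol/l per g/dl.
- The two conversions differ by a factor of 2. On the 0.625 scale, 10 g/dl is 10 × 0.625 = 6.25 mmol/l, and 12.5 mmol/l is 12.5 / 0.625 = 20 g/dl.

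**Step 5: does the design depend on these figures?** No. The Section 19.4 rule (9 or more responses in 19) has an exact one-sided error of 0.084 at a 30% response rate and power of 0.912 at 60%. Both agree with the stated 0.1 and 90%, and neither uses calcium or hemoglobin.

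**The case against.** The best reply is that this is a faulty unit conversion with little practical reach. Most of that stands.

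- **The word *or*.** A reader might infer that the lower value is a second, sufficient route to progression. The documents do not support that. Appendix D puts the SI figure in brackets as an equivalent, so the natural reading of Section 16.1 is one threshold stated in two units. The defect is that the two statements disagree.
- **A number in the band is not enough.** A reader might take any calcium between the two values as progression in SI units. The criterion also requires that the hypercalcemia be new and attributable solely to the plasma cell disorder.
- **The unit.** The protocol mostly uses conventional units and prints mg/dL first. Its references to HIPAA and to patients' insurance carriers suggest US sites, though that is an inference. If all laboratories report mg/dL and nobody converts, the conflict does not arise.
- **The primary result.** A reader might infer that one misjudged progression could tip the 9-of-19 decision. Nothing shows this. Section 19.4 measures response by immunoglobulins, light chains and electrophoresis; calcium enters only through the no-progression condition. It would take a patient who would otherwise respond, with new myeloma-only hypercalcemia inside a 0.88 mg/dL band, judged in mmol/L. PFS itself is secondary and summarized by Kaplan-Meier methods.
- **Hemoglobin.** A reader might infer that almost anyone would qualify as anemic in SI units. Appendix D also requires an M-component (or its stated substitutes) with clonal plasma cells or a plasmacytoma, and attribution to the plasma cell disorder. Footnote c gives the correct 100 g/l. Enrolled patients already have relapsed or refractory myeloma, and no inclusion criterion cites the appendix.

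What the reply does not remove is the mismatch itself. It sits in an operative endpoint definition, it appears in two places, and no text resolves it.

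**Conclusion.** The point holds as a wrong figure in the definition of progression. The two calcium thresholds differ by about 0.88 mg/dL (0.22 mmol/L, 8%). For a new corrected calcium between them that is attributed solely to the myeloma, progression depends on the unit used. That can affect PFS and, through Section 16, response.

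The expected number of patients is small: few or none if all laboratories report mg/dL, which is an assumption. The sample size and the error rates of the decision rule are unaffected, and no change to the 9-of-19 decision has been shown. The arithmetic rests only on the molar mass of calcium and is stable over the range tried. It says nothing about which calcium threshold is clinically right.

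The hemoglobin slip is editorial. Hemoglobin is not a progression criterion, and the appendix serves only to document an established diagnosis at baseline.

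**What to change.** Reconcile the calcium pair in Section 16.1 and Appendix D. The sponsor should state which value governs, then either convert the other exactly or delete it:

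- if 11.5 mg/dL governs, the SI figure is 2.87 mmol/L;
- if 2.65 mmol/L governs, the conventional figure is 10.6 mg/dL.

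At the same time, correct the hemoglobin SI figure in Appendix D, in both the anemia criterion and footnote c. On the appendix's own scale of 2 g/dl to 1.25 mmol/l, 10 g/dl is 6.25 mmol/l.

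That makes four text entries: calcium in two places and hemoglobin in two. No visit, sample or data item changes. Revisions need IRB approval before use (Section 18.3), including at each site (Section 6), so the change is cheapest when carried in the next amendment.

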## 16.2. FreeLite™ Disease Response Criteria

- **Complete Response:** For those patients being followed by serum free light chain (and NO measurable serum or urine M-spike), which were immunofixation negative, normalization of serum free light chain ratio.
  - Normalization is defined as the serum free light chain ratio being within the normal range. If the serum free light chain ratio is not within the normal range, but the individual kappa and lambda light chain values are within normal range, this may be considered CR.
- **Partial Response:** If only measurable parameter is serum immunoglobulins free light chain (FLC), EITHER of the following changes qualify as partial response:
  - A 50% decrease in the difference between involved and uninvolved FLC levels;

*OR*

- A 50% decrease in the level of involved FLC AND a 50% decrease (or normalization) in the ratio of involved/uninvolved FLC.

- **Progressive Disease:** If only measurable parameter is serum immunoglobulins free light (FLC), either of the following qualify as progression:
  - 50% increase in the difference between involved and uninvolved FLC levels from the lowest response level, which must also be an absolute increase of at least 10 mg/dL;

*OR*

- 50% increase in the level of involved FLC AND a 50% increase in the ratio of involved/uninvolved FLC from the lowest response level.

## 16.3. Measurable Disease Parameter

Measurable disease is disease that can be measured either by serum or urinary evaluation of the monoclonal component or by serum assay of FLC and is defined by at least one of the following three measurements:

- Serum M-protein  $\geq 0.5$  g/dl
- Urine M-protein  $\geq 200$  mg/24 h
- Serum FLC assay: Involved FLC level  $\geq 10$  mg/dl ( $\geq 100$  mg/l) provided serum FLC ratio is abnormal

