### **3. INCLUSION AND EXCLUSION CRITERIA**

#### **3.1. Inclusion Criteria**

To be included in this study, participants must meet the following criteria:

1. Patients with multiple myeloma who have relapsed (or who are primary refractory) following treatment with a proteasome inhibitor-containing regimen (excluding ixazomib), and who have not been treated with a second proteasome inhibitor (ixazomib, bortezomib, carfilzomib, or other proteasome inhibitor).
2. Age  $\geq$  18 years of age at time of consent.
3. Have an ECOG Performance Status of  $\leq$  2 at study entry. Refer to **Appendix A**.
4. Must be free of systemic infection:
  - Subjects with active infections (whether or not they require antibiotic therapy) may be eligible after complete resolution of the infection.
  - Subjects on antibiotic therapy must be off antibiotics for at least 7 days before beginning treatment.
5. Have the following clinical laboratory values:
  - Absolute neutrophil count  $\geq$  750/mm^3
  - Platelet count  $\geq$  25,000/mm^3
  - Creatinine clearance  $\geq$  30 mL/min
  - Total bilirubin: AST (SGOT) and ALT (SGPT)  $\leq$  3x ULN
6. Patient's multiple myeloma cells are positive for CD28 or CD86 expression by flow cytometry or immunohistochemistry (in any proportion). CD28 or CD86 positivity can have been determined on previous bone marrow aspirates or biopsies.
7. Disease free of prior malignancies for  $>2$  years with exception of currently treated basal cell, squamous cell carcinoma of the skin, or carcinoma "in situ" of the cervix or breast.
8. Participants of child-bearing potential must agree to use adequate contraceptive methods (e.g., hormonal or barrier method of birth control; abstinence) prior to study entry. Should a woman become pregnant or suspect she is pregnant while she or her partner is participating in this study, she should inform her treating physician immediately.
9. Participant must understand the investigational nature of this study and sign an Independent Ethics Committee/Institutional Review Board approved written informed consent form prior to receiving any study related procedure.

Refer to **Appendix B** for the ELIGIBILITY VERIFICATION FORM: INCLUSION CRITERIA CHECKLIST.

Roswell Park Protocol No.: I 47217

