### **3.2. Exclusion Criteria**

Participants will be excluded from this study for the following:

1. Prior treatment with ixazomib.
2. Inability to take ixazomib or abatacept.
3. Life expectancy less than 4 months.
4. Patients with a known diagnosis of plasma cell leukemia.
5. Known active tuberculosis or fungal infection.
6. Known seropositive for or active viral infection with, human immunodeficiency virus (HIV), hepatitis B virus (HBV), or hepatitis C virus (HCV). Patients who are seropositive because of immunization with the hepatitis B virus vaccine are eligible.
7. Uncontrolled intercurrent illness including, but not limited to, ongoing or active infection, symptomatic congestive heart failure, unstable angina pectoris, cardiac arrhythmia, or psychiatric illness/social situations that would limit compliance with study requirements.
8. Any condition, including the presence of laboratory abnormalities, which places the subject at unacceptable risk if he/she were to participate in the study or, which confounds the ability to interpret data from the study.
9. Pregnant or nursing female participants.
10. Unwilling or unable to follow protocol requirements.
11. Any condition which in the Investigator's opinion deems the participant an unsuitable candidate to receive study drug.
12. Received an investigational agent within 30 days prior to enrollment.

Refer to **Appendix C** for the ELIGIBILITY VERIFICATION FORM: EXCLUSION CRITERIA CHECKLIST.

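### No entry criterion requires the measurable disease that Section 16.3 defines, and End of Treatment has no serum or urine panel to confirm a response first seen at the last draw

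*Combined protocol and SAP*

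**What the plan says.** **Entry.** Section 16.3 says that "Measurable disease is disease that can be measured either by serum or urinary evaluation of the monoclonal component" or by FLC assay. It asks for at least one of: serum M-protein of 0.5 g/dl or more, urine M-protein of 200 mg/24 h or more, or involved FLC of 10 mg/dl or more with an abnormal ratio. The disease criterion in Section 3.1, item 1, is "Patients with multiple myeloma who have relapsed (or who are primary refractory) following treatment with a proteasome inhibitor-containing regimen". It cites neither 16.3 nor the progression criteria of 16.1. Nothing else in Sections 3.1 and 3.2 or the Appendix B and C checklists sets a measurable-disease threshold. The nearest is exclusion 8, a discretionary clause covering any condition "which confounds the ability to interpret data from the study".

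Section 11.2 asks for "Documentation of pathological diagnosis (see International Myeloma Working Group (IMWG) Diagnostic Criteria: Appendix D". Footnote a of that appendix admits non-secretory myeloma: for patients "with no serum or urine M-component and normal serum FLC ratio, the baseline bone marrow must have" at least 10% clonal plasma cells.

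**PR with nothing measurable.** When M-protein and FLC are both unmeasurable, Section 16.1 says that a plasma-cell reduction of 50% or more "is required in place of M-protein, provided baseline bone marrow plasma cell percentage was" 30% or more. The baseline marrow is at the investigator's discretion. Section 3.1, item 6, allows that "CD28 or CD86 positivity can have been determined on previous bone marrow aspirates or biopsies", and Section 11.2 adds: "A fresh sample is not required if CD28 or CD86 positivity has been determined on a previous bone marrow aspirate or biopsy".

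**Confirmation.** Section 16 requires two consecutive assessments for every response category, at any time before new therapy. The serum and urine panel is scheduled at baseline and on Day 1 of each cycle from Cycle 2 (Sections 11.2 and 11.3, Appendix E). Section 11.6 does not list it, and the End of Treatment cells of the five panel rows in Appendix E are blank. After treatment it is required only for Stringent CR (Section 11.7; Appendix E, footnote 20).

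**Analysis.** Section 19 includes all patients who receive or attempt treatment. Section 19.4 calls the regimen promising at 9 or more responses in 19. Its replacement rule deals only with withdrawal before the end of Cycle 1.

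**The concern.** The primary endpoint is a count of documented responses in 19 patients against a fixed cut-off of 9. The plan can admit a patient whose response it has limited means to record, and it can leave a true response with only one of the two assessments it requires. If either patient is scored as a failure, the observed rate falls for a reason unrelated to the treatment. With 19 patients, one lost response matters: the design clears its stated 90% power by about one percentage point.

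**Working it through.** **1. Who can enrol below all three thresholds.** The progression criteria in 16.1 ask for absolute rises of at least 0.5 g/dL (serum M-protein), 200 mg/24 h (urine M-protein) or 100 mg/L (FLC difference). These match the 16.3 levels (10 mg/dl = 100 mg/l). A patient whose relapse met one of them would usually be at or above a 16.3 threshold at relapse. The exceptions are primary refractory disease and relapse shown by marrow, bone lesion, plasmacytoma or hypercalcemia, all of which inclusion 1 allows.

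**2. What such a patient can score, if truly non-secretory.**
- Marrow plasma cells 10% to under 30%: accepted by Appendix D, but the PR fallback in 16.1 needs a baseline of 30% or more. There is no PR route.
- 30% or more: the route exists, but the baseline marrow is discretionary and no on-treatment marrow is scheduled to show PR.
- CR remains possible in both groups.

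**3. Which responses lack a second scheduled assessment.** A responder who continues is confirmed at the next Day 1, 28 days later. The exposed case is a PR or VGPR first seen at the last Day 1 draw before a stop without progression, for example for toxicity, which Section 12.1 lists as a reason.

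**4. The plan's own figure.** Inputs from 19.1 and 19.4: n = 19, null rate 0.30, alternative 0.60, success at 9 or more, one-sided alpha 0.10. Exact binomial:
- Type I error: P(X ≥ 9 | 19, 0.3) = 0.084. A cut-off of 8 gives 0.182, so 9 is the smallest valid cut-off.
- Power: P(X ≥ 9 | 19, 0.6) = 0.912, against the stated 90%. Reproduced.

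**5. Worst case for the entry gap (assumed numbers of patients).** Let k of 19 have zero chance to score and count as non-responders. The probability of success is P(X ≥ 9 | 19 − k, p).

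| k | Power, p = 0.6 | Power, p = 0.5 | Type I error, p = 0.3 |
|---|---|---|---|
| 0 | 0.912 | 0.676 | 0.084 |
| 1 | 0.865 | 0.593 | 0.060 |
| 2 | 0.801 | 0.500 | 0.040 |
| 3 | 0.716 | 0.402 | 0.026 |

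The 50% column is the lower end of the range that 19.1 calls clinically relevant.

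**6. A milder case.** Suppose one such patient keeps a response probability q (assumed) and the other 18 respond at 0.6. Then power = P(X ≥ 9 | 18, 0.6) + q × P(X = 8 | 18, 0.6). The second probability is 43,758 × 0.6^8 × 0.4^10 = 0.0771. So power = 0.8653 + 0.0771q, which is 0.873, 0.881 or 0.888 for q = 0.1, 0.2 or 0.3.

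**7. The confirmation gap (assumed rates).** Here a fraction of responses is lost, not whole patients. If 5% of true responses go unconfirmed, the observable rate is 0.6 × 0.95 = 0.57 and power is 0.860. At 10% the rate is 0.54 and power is 0.791. Under the null, type I error falls to 0.063 and 0.046.

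**The case against.** The strongest reply is that both gaps are narrow. Relapse by M-protein or FLC usually brings a patient to a 16.3 level, so the entry gap is residual. Panels run every 28 days, and an unscheduled test before new therapy would count, so the confirmation gap touches only a response first seen at the last draw. The documents give no frequency for either. All of this stands, and it limits the size of the point. It does not close the gaps: inclusion 1 does not cite the progression criteria, and nothing prompts the unscheduled test.

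A reader might infer four stronger things that the documents do not support.
- **Anyone below the 16.3 thresholds can reach PR only through the marrow.** Section 16.1 does not define unmeasurable or tie it to 16.3. A detectable M-protein below 0.5 g/dl could, on the literal text, halve, and the immunofixation limb of VGPR has no baseline threshold. The missing PR route is secure only for truly non-secretory disease under 30%.
- **The losses in step 5 are expected losses.** They assume zero chance to score, although CR stays possible. They are worst cases, and they do not describe the confirmation gap. Falling below 90% is also weak evidence by itself, because the design has only about one point to spare.
- **Section 19.4 makes these patients non-responders.** For patients past Cycle 1 this is an inference from the analysis set in Section 19 and the replacement rule in 19.4. It is not stated.
- **Marrow at the end of treatment is limited to progression or confirmation of CR or Stringent CR.** Section 11.6 reads that way, but Section 11.9.2 also schedules it at off study, and Section 8.3 has a similar off-study clause for CD28/CD86. One off-study marrow would still not supply two consecutive assessments.

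**Conclusion.** The concern holds in limited form. The plan defines measurable disease without requiring it, and requires confirmation without always scheduling it. Followed as written, it can leave a true response undocumented.

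If the affected patients count as non-responders, the error is conservative: power falls and type I error is not inflated. At a true rate of 60%, power falls from 0.912 to between 0.865 and 0.716 in the worst case of 1 to 3 patients. It is 0.873 to 0.888 if one such patient keeps a response probability of 0.1 to 0.3. It is 0.860 or 0.791 if 5% or 10% of responses go unconfirmed. All these inputs are assumed. The stated sample size and power are correct; the weakness is in how the endpoint is ascertained. The change should be made because it is cheap relative to a response lost under a 9-of-19 rule.

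**What to change.** 1. **Panel.** Add the disease status panel (quantitative immunoglobulins, SPEP, serum IFE, serum FLC, 24-hour UPEP and UIFE) to Section 11.6 and to the End of Treatment column of Appendix E. Cost: one blood draw and one 24-hour urine per patient, at most 19 extra panels. The visit already draws blood.
2. **Entry.** Add to Section 3.1 and Appendix B: measurable disease at baseline by at least one criterion in Section 16.3. Cost: about 2.5 months of accrual per excluded patient (48 months / 19 = 2.53), hence 5.1 or 7.6 months for two or three. The documents do not say how many this would be. Excluded patients lose access to the trial, including non-secretory patients at 30% or more plasma cells, who do have a PR route on paper. The sponsor should accept that knowingly.
3. **Counting rule.** State in Section 19.4 that patients past Cycle 1 without a confirmed response count as non-responders. This costs nothing and settles what is now inferred.
4. **Marrow timing.** Reconcile Section 11.6 with Sections 11.9.2 and 8.3 on when the end-of-treatment marrow is taken.

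The target of 19 and the cut-off of 9 stay as they are. Items 1 to 3 add no biopsy.
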